10.2. Statistical Methodology

A full statistical plan will be finalized before database lock.

The primary efficacy analysis will be performed after all patients have finished 6 months of treatment with study drug.

Analyses will be performed using SAS[®] for Windows (version 9.2 or higher). Descriptive statistics (mean, standard deviation, median, minimum, and maximum) will be presented for continuous variables, and frequencies and percentages will be presented for categorical and ordinal variables. Percentages will be based on the number of nonmissing values in the dose group. All study data will be presented in by-patient/patient data listings.

10.2.1. Populations to be Analyzed

The populations (analysis sets) are defined as follows:

Evaluable Analysis Set: All patients who have received at least one dose of study drug and have a non-missing serum TTR result at the Month 6 (Week 26) visit.

Safety Analysis Set: All patients who received at least a single dose of study drug.

PK Analysis Set: All patients who received at least a single dose of study drug and have at least 1 postdose blood sample for PK parameters and who have evaluable PK data.

The primary population used to evaluate efficacy will be the Evaluable Analysis Set. Safety will be analyzed using the Safety Analysis Set. The PK Analysis Set will be used to conduct PK analyses.

10.2.2. Baseline Evaluations

Demographic and key disease characteristics data will be summarized. Data to be tabulated consist of gender, age, ethnicity, and race, as well as other key disease characteristics.

10.2.3. Efficacy Analyses

10.2.3.1. Primary Efficacy Endpoint

The primary efficacy endpoint is the percent reduction from baseline in serum TTR level at 6 months. This analysis will be a 2-sided 95% CI for the mean of the primary endpoint. A t-test,

in which the null hypothesis of no reduction is compared against the alternative hypothesis of a change, will also be performed.

Sensitivity analyses, including different methods for handling the missing data, will assess the robustness of the primary endpoint for the Evaluable Analysis Set.

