#### 1.1.2. Document and Study Objectives

This statistical analysis plan (SAP) is designed to outline the methods to be used in the analysis of study data in order to address the study objectives. Populations for analysis, data handling rules, statistical methods, and formats for data presentation are provided. The statistical analyses and summary tabulations described in this SAP will provide the basis for the results sections of the clinical study report (CSR) for this trial.

This SAP will also outline any substantial differences in the currently planned analyses relative to those planned in the study protocol (see Section 5). Any substantial changes made to the planned analyses after finalization of the SAP will be described in the CSR.

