# 2. PATIENT POPULATION

# 2.1. Population (Analysis Set) Definitions

The following patient populations (analysis sets) will be evaluated and used for presentation and analysis of the data:

- Evaluable Analysis Set: All patients who have received at least a single dose of study drug and have a non-missing serum TTR result at Month 6 (Week 26) visit.
- Safety Analysis Set: All patients who received at least a single dose of study drug.
- PK Analysis Set: All patients who received at least a single dose of study drug and have at least 1 postdose blood sample for PK parameters and who have evaluable PK data.

The primary efficacy endpoint will be analyzed using the Evaluable Analysis Set. All secondary and exploratory efficacy endpoints will be analyzed using the Evaluable Analysis Set and Safety Analysis Set (note: if these 2 analysis sets are identical then secondary and exploratory efficacy endpoints will be analyzed using only the Evaluable Analysis Set). Safety will be analyzed using the Safety Analysis Set. The PK Analysis Set will be used to conduct PK analyses. PK analyses are described in a separate PK analysis plan.

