### 3.10. Missing Data

In general, there will be no substitutions made to accommodate missing data points. All data recorded on the electronic case report form (eCRF) will be included in data listings that will accompany the CSR. Data collected at multiple time points throughout the study will be presented in chronological order in the data listings according to assessment date/time. Data summaries and analyses will be based on observed data only.

Methods for handling incomplete or missing components of efficacy endpoints are discussed in the endpoint scoring algorithms in Section 6.

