## 3.11. Visit Windows

It is expected that all visits should occur according to the protocol schedule. All data will be tabulated per the evaluation visit as recorded on the eCRF even if the assessment is outside of the visit window.

Data collected at unscheduled visits will be included in by-patient data listings, but no assignment to a study visit will be made for the purpose of by-visit summary tabulations. However, unscheduled visits will be considered for computation of baseline values, as discussed in Section 3.4, and for inclusion in any categorical shift summaries (e.g., shift from baseline to "worst" post-baseline value).

The relative day of all dates will be presented in data listings.

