### 4.3. Efficacy Analysis

#### 4.3.1. Primary Efficacy Endpoint

The primary efficacy analysis will be performed after all patients have finished 6 months of treatment with study drug. The primary efficacy analysis will be based on the Evaluable Analysis Set.

The primary efficacy endpoint is the percent change from baseline in serum TTR level at 6 months. The mean percent change in serum TTR from baseline to 6 months with the associated 95% CI will be presented. A 2-sided 80% CI will also be generated. A t-test of the null hypothesis of no change in serum TTR from baseline at 6 months will be performed at the 2-sided, 0.05 confidence level.

Sensitivity analyses will be conducted to assess the robustness of the primary analysis. The sensitivity analyses will include a bootstrap 95% CI for the median percent change from baseline to 6 months in serum TTR. The bootstrap CI will be constructed using the percentile method. That is, the lower and upper limits of the bootstrap CI are defined as the 2.5th and 97.5th percentiles of the median percent change from baseline estimated from 1000 bootstrap samples. In addition to the t-test described above, a sensitivity analysis will include the p-value from the Wilcoxon signed rank test.

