#### 4.3.2. Secondary Efficacy Endpoints

Analyses of secondary efficacy endpoints will be based on the Evaluable Analysis Set and Safety Analysis Set, except as noted in Section 2.1.

Descriptive statistics for actual values, change from baseline, and percent change from baseline at each scheduled visit will be provided for serum TTR. Eighty percent and 95% CIs will be produced for the mean change from baseline at Month 18. Individual serum TTR values over time will be plotted. Individual values of percent change from baseline in serum TTR will also be plotted. Plots of the mean ( $\pm$  SEM) serum TTR values and percent change in serum TTR from baseline at each scheduled visit will be generated.

Descriptive statistics will be provided for actual values, change from baseline, and percent change from baseline at each scheduled visit for the mNIS+7 composite score, and the Norfolk QOL-DN total score. Both 80% and 95% CIs will be produced for the mean change from baseline at Month 18 for these endpoints.

Components of the mNIS+7 will be summarized separately, including the NIS-Weakness, NIS-Reflexes, Nerve conduction (sum of the 5 NCS), quantitative sensory testing (QST), and postural blood pressure Similar descriptive summaries will be provided for the 5 domain scores of the Norfolk QOL-DN (see Section 6.2).

Shift tables will be created for the PND score to summarize the baseline value versus post-baseline value at each scheduled visit. An additional summary of PND score will present the shift from baseline to worst post-baseline value.

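### Read literally, the missing-data sensitivity analyses act on a set with no missing Month 6 TTR, and the available SAP text names no analysis that brings in dosed patients without that value

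*Protocol*

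**What the plan says.** Protocol 10.2.3.1 makes the primary analysis a 95% confidence interval for the mean percent reduction in serum TTR at Month 6, with a t-test alongside, and adds: "Sensitivity analyses, including different methods for handling the missing data, will assess the robustness of the primary endpoint for the Evaluable Analysis Set".

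The Evaluable Analysis Set consists of dosed patients who "have a non-missing serum TTR result at the Month 6 (Week 26) visit" (Protocol 10.2.1). SAP 2.1 repeats the condition: "have a non-missing serum TTR result at Month 6 (Week 26) visit".

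On sensitivity, SAP 4.3.1 says "The sensitivity analyses will include a bootstrap 95% CI for the median percent change from baseline to 6 months in serum TTR" and adds a Wilcoxon signed rank p-value. On missing data, SAP 3.10 makes no substitutions in general and says "Data summaries and analyses will be based on observed data only". On visits, SAP 3.11 says "All data will be tabulated per the evaluation visit as recorded on the eCRF even if the assessment is outside of the visit window", and assigns unscheduled samples to no visit in the by-visit summaries. SAP 4.3.2 provides "Descriptive statistics for actual values, change from baseline, and percent change from baseline at each scheduled visit will be provided for serum TTR" on both the Evaluable and Safety Sets, plus individual TTR plots.

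SAP 1.1.2 undertakes to "outline any substantial differences in the currently planned analyses relative to those planned in the study protocol" and points to Section 5. Section 5 lists none; it says that changes will be summarized in the study report.

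Protocol 4.4 allows patients who withdraw before 6 months to be replaced.

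**The concern.** The protocol promises a check on how the primary estimate depends on missing data, and attaches it to a set from which every patient with a missing Month 6 value has already been removed. A dosed patient who leaves early or misses the Week 26 sample drops out of the primary analysis and may be replaced. No available text then carries that patient into any Month 6 estimate.

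This matters because the estimate is the primary analysis and is what the study was sized on. With about 12 patients, one or two exclusions are a sizeable share of those dosed. The group affected is narrow: dosed patients with no Week 26 result.

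**Working it through.** **1. The definitions.** Membership requires a non-missing Week 26 TTR, so the number of missing Week 26 values in the Evaluable Set is 0 at any dropout rate. The percent change could still be missing if a patient had no pre-dose TTR at all. Baseline averages all pre-dose values (SAP 3.4) and several are scheduled, so that case is remote.

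**2. What the SAP offers instead.**
- The bootstrap interval and the Wilcoxon test use the same patients. They examine distribution shape and outliers, not missing data.
- The Safety Set summary of TTR by visit uses observed data. Its Month 6 row holds the patients with a Week 26 value, who are the Evaluable Set again. An out-of-window sample recorded as Month 6 counts in both.
- The cross-reference in SAP 3.10 to Section 6 concerns scoring of incomplete components; no TTR rule appears there.

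**3. The plan's own precision figure** (Protocol 10.1; n = 12, mean 80%, SD 6%).
- Normal quantile: 80 ± 1.96 × 6/√12 = 80 ± 3.4, or 76.6 to 83.4. This rounds to the stated 77% to 83%.
- t quantile, 11 df: 80 ± 2.201 × 6/√12 = 80 ± 3.8, or 76.2 to 83.8.

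**4. Possible size.** These are assumptions: the documents give neither a dropout rate nor TTR values for such patients. Take n observed patients at mean 80, SD 6, and k missing patients who all have reduction v, with N = n + k.

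mean = (80n + kv)/N

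SS = (n − 1) × 36 + n(80 − mean)² + k(v − mean)²

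CI = mean ± t(0.975, N − 1) × √[SS/(N − 1)]/√N

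Example, n = 11, k = 1, v = 70:
- mean = 950/12 = 79.2
- SS = 360 + 7.6 + 84.0 = 451.7, so SD = 6.41
- half-width = 2.201 × 6.41/√12 = 4.07, so the CI is 75.1 to 83.2

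With 12 dosed:

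| Reduction in missing patients | 1 missing (n = 11) | 2 missing (n = 10) |
|---|---|---|
| Evaluable Set as planned | 80.0 (76.0 to 84.0) | 80.0 (75.7 to 84.3) |
| 80% | 80.0 (76.4 to 83.6) | 80.0 (76.6 to 83.4) |
| 70% | 79.2 (75.1 to 83.2) | 78.3 (74.1 to 82.6) |
| 40% | 76.7 (68.5 to 84.9) | 73.3 (62.9 to 83.8) |
| 0% | 73.3 (58.2 to 88.5) | 66.7 (46.6 to 86.8) |

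If withdrawn patients are replaced so that 12 are evaluable, one or two replaced patients at 0% give 73.8% (60.0 to 87.7) or 68.6% (51.5 to 85.6).

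**5. Break-even.** With 12 dosed the shift is k(80 − v)/12.
- Above 3 points: v < 80 − 36/k, which is 44% for one missing patient and 62% each for two.
- Above the t-based 3.8 points: v < 80 − 45.6/k, which is about 34% and 57%.

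**6. The t-test.** The largest p-value in these scenarios is 1.5 × 10⁻⁵ (two missing of 12 dosed, both at 0%).

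**The case against.** **The sentence has another reading.** It can mean that the Evaluable Set result is the thing tested and that the alternatives may use other patients. The protocol never confines them to that set, and Protocol 10.2 defers detail to the full statistical plan. This is fair. It shifts the gap to the SAP without closing it, because the available SAP text names no such alternative.

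**The SAP copy is incomplete.** The pages before its table of contents were removed, and the table, figure and listing inventories in Section 7 survive only as headings. A planned sensitivity table could have been listed there. The wording in SAP 4.3.1 and 3.10 also leaves room for more. This stands: the mismatch in definitions is certain, while the SAP's silence is established only for the text available.

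**Planned outputs already show these patients.** Individual TTR plots and listings will display the course of each dosed patient wherever samples exist, and SAP 4.1 tabulates the size of each analysis set. This also stands. With about 12 patients a reader will see who is left out, but will get no Month 6 estimate that includes them.

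**The effect may be small.** At 70% to 80% reduction the mean moves by 0 to 1.7 points. Larger shifts need values that the documents do not supply.

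**Stronger readings that the documents do not support:**
- A reader might infer that the sensitivity analyses test nothing. The bootstrap and Wilcoxon analyses do test dependence on distribution shape.
- A reader might infer that anyone who stops drug or has a dose reduction is lost. Protocol 4.3 encourages those who stop to complete assessments, and nothing in the set definition removes a patient who gives the Week 26 sample.
- A reader might infer from Section 5 that the sponsor deliberately dropped the analysis. Section 5 lists no change and gives no reason; it shows only that no departure was recorded there.

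**Conclusion.** The point holds in limited form. Taken literally, the promised missing-data check cannot differ from the primary result. Taken more generously, it is not specified in the SAP text available. It should be fixed, though it does not threaten the study's conclusion about whether TTR falls. A reader might infer that the hypothesis test is at risk; it stays at p < 0.001 in every scenario shown, and no success threshold for the mean is stated.

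What is exposed is the mean and its interval. The size rests wholly on assumed values: negligible if missing patients respond much like the rest, and beyond the planned precision only if one responds below about 44%, or two below about 62% each (34% and 57% on the t-based half-width). Which case applies cannot be known in advance, which is the reason to specify the check now.

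**What to change.** Revise the SAP; the primary analysis and the Evaluable Set stay as they are.

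1. In SAP 4.3.1, add one Month 6 sensitivity analysis on the Safety Analysis Set, including replaced patients. If Week 26 TTR is missing, use the Week 24 sample (already scheduled, Protocol Table 1, footnote m). If that is also missing, use the last observed post-dose TTR, including Early Termination. Count separately any patient with no post-dose TTR.
2. As a labelled worst-case bound, repeat it with 0% reduction for dosed patients who have neither a Week 26 nor a Week 24 value. State that this overrides any earlier observed value, and that its interval is wider in both directions (58.2 to 88.5 against 76.0 to 84.0 with one missing), so it bounds the mean rather than giving a uniformly conservative interval.
3. Report the number of replaced patients beside the set counts already planned in SAP 4.1.
4. State in SAP 3.10 and 3.11 that this analysis is an exception to the observed-data and recorded-visit rules.
5. Record in SAP Section 5 that it replaces the protocol's missing-data analysis on the Evaluable Set.

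The cost is a short SAP revision and a few table rows, with no new samples or patients. The protocol sentence can be corrected when the protocol is next amended for other reasons. The drawbacks are an all-dosed estimate that may be lower and wider, and a last observed TTR that may overstate the reduction once drug has been stopped, which is why the 0% bound accompanies it.

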10.2.3.2. Secondary Efficacy Endpoints

The secondary endpoints of the study are the change from baseline over 18 months for the following: serum TTR, mNIS+7, Norfolk QOL-DN, and PND score.

For continuous parameters, measurements will be summarized using descriptive statistics. Actual measurement, change, and percentage change from baseline to each scheduled visit will be summarized. To understand the effect of revusiran, the mean change from baseline at 18 months with the associated 80% and 95% CIs will also be summarized.

For categorical parameters, frequencies and percentages will be presented. To understand the effect of revusiran from baseline, the frequency and percentage of patients at each of the category shifts from baseline at 18 months will be summarized.

10.2.3.3. Exploratory Endpoints

The exploratory endpoints of the study are to assess the change from baseline over 18 months for the following: mBMI, FAP stage, NIS, a grip strength test, NYHA classification, Karnofsky Performance Status, ECHO parameters, cardiac biomarkers, EQ-5D and COMPASS 31 questionnaires, and an optional exploratory residual liver tissue evaluation, if available. Analyses for these endpoints will be conducted in a similar fashion as specified for secondary efficacy endpoints.

10.2.4. Safety Analyses

Safety assessments include AEs (including liver allograft rejection), clinical laboratory parameters (hematology and serum chemistry, including liver function tests, renal function, thyroid function, coagulation, and urinalysis), vital signs (oral body temperature, blood pressure, heart rate, and respiration rate), 12-lead ECGs, physical and ophthalmologic examinations, and concomitant medications (including immunosuppressive agent monitoring).

10.2.4.1. Adverse Events

Adverse events will be summarized by MedDRA System Organ Class and Preferred Term. Separate tabulations will be generated for treatment-emergent AEs (TEAEs), TEAEs by maximum severity, treatment-related AEs, SAEs, and discontinuation of study drug due to AEs. A patient listing will be produced for all AEs, deaths, SAEs, and AES leading to discontinuation of study drug.

10.2.4.2. Vital Signs, Clinical Laboratory Safety Tests, 12-lead Electrocardiograms, Physical and Ophthalmologic Examinations

For each continuous laboratory safety parameter (including, but not limited to, hematology, serum chemistry, coagulation, and urinalysis) results will be categorized as low, normal, or high based on the laboratory normal ranges. Shifts from baseline laboratory grade to the maximum

laboratory grades will be examined for key safety parameters. All out-of-range and clinically significant laboratory results will be identified in data listings. Descriptive statistics will also be provided as actual value and change from baseline over time.

Descriptive statistics for vital signs and ECG interval data will be presented by actual values and changes over time from baseline. Details of any abnormalities will be included in the data listings.

For ophthalmologic examinations, descriptive statistics of changes in eye examinations from baseline over time will be presented. Separate listings will be generated for any abnormalities noted during the eye examination.

10.2.4.3. Concomitant Medications

All concomitant medications collected from screening through the study period will be classified to preferred terms according to the World Health Organization (WHO) drug dictionary. Additional safety analyses will focus on therapy, frequency, and dose of immunosuppressive agents.

11. DIRECT ACCESS TO SOURCE DATA/DOCUMENTS

11.1. Study Monitoring

The clinical monitor, as a representative of the Sponsor, has an obligation to follow the study closely. In doing so, the monitor will visit the Investigator and clinical study center periodically as well as maintain frequent telephone and written contact. The monitor will maintain current personal knowledge of the study through observation, review of study records, and source documentation and discussion of the conduct of the study with the Investigator and staff. All aspects of the study will be carefully monitored by the Sponsor or its designee for compliance with applicable government regulations in respect to Good Clinical Practice (GCP) and current standard operating procedures.

11.2. Audits and Inspections

Authorized representatives of Alnylam Pharmaceuticals, Inc., a regulatory authority, an IEC, or an IRB may visit the clinical study center to perform audits or inspections, including source data verification. The purpose of an Alnylam Pharmaceuticals, Inc. audit or inspection is to systematically and independently examine all study-related activities and documents to determine whether these activities were conducted and data were recorded, analyzed, and accurately reported according to the protocol, GCP guidelines of the International Conference on Harmonization (ICH), and any applicable regulatory requirements. The Investigator should contact Alnylam Pharmaceuticals, Inc. immediately if contacted by a regulatory agency about an inspection.

11.3. Institutional Review Board

The Principal Investigator must obtain IRB/IEC approval for the investigation. Initial IRB/IEC approval and all materials approved by the IRB/IEC for this study including the patient ICF and recruitment materials must be maintained by the Investigator and made available for inspection.

11.4. Quality Control and Quality Assurance

Study staff is expected to adhere to the following practices governed by GCP and all applicable regulatory requirements. To ensure these practices are in place, the Sponsor may conduct a quality assurance audit.

The Investigator will submit reports of SAEs as outlined in this protocol. In addition, the Investigator agrees to submit progress reports to his/her IRB or IEC per their local reporting requirements, or at least annually and at the conclusion of the study. The reports will be made available to the Sponsor or designee.

Deviations from the protocol necessary to protect patient safety should be reported to the CRO within 24 hours of knowledge of the event.

Any communications from regulatory agencies in regard to inspections or other studies that impact this protocol or the qualifications of study staff should be promptly reported to the CRO.

Major changes in this research activity, except those to remove an apparent immediate hazard to the patient, must be reviewed and approved by the Sponsor and the IRB or IEC that approved the study. Amendments to the protocol must be submitted in writing to the Investigator's IRB or IEC and the Regulatory Authority for approval before patients are enrolled under the amended protocol.

Regulatory authorities will receive the protocol, amendments, reports on SAEs, and the Integrated Clinical Trial Report according to national and any local regulations.

